1.0 Objectives

We will leverage increasingly available technologies to impart a Universal Medication Schedule (UMS) in primary care to help patients living with diabetes safely use and adhere to complex drug regimens. We will conduct a 3-arm, multi-site trial to:

1.1 Specific Aims:

1. Test the effectiveness of the UMS, and UMS + SMS text reminder strategies compared to usual care.
2. Determine if the effects of these UMS strategies vary by patients' literacy skills and language.
3. Using mixed methods, Evaluate the fidelity of the two strategies and explore patient, staff, physician, and health system factors influencing the interventions.
4. Assess the costs required to deliver either intervention from a health system perspective.

1.2 Hypotheses:

1. Compared to usual care, patients receiving the UMS or UMS+SMS text reminder strategies will demonstrate a better understanding of how to safely dose their Rx regimen
2. Compared to usual care, patients receiving the UMS or UMS+SMS text reminder strategies will when possible, take their Rx regimen fewer times per day
3. Compared to usual care, patients receiving the UMS or UMS+SMS text reminder strategies will have greater adherence to their Rx regimen
4. Compared to the UMS only arm, patients receiving the UMS+SMS strategy will have greater adherence to their Rx regimen.
5. The intervention effects will be greater among those with limited literacy and English proficiency.

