Medication Adherence	ASK-12	Matza, 2009	x	x	x
	24-hour recall		x	x	x
	Pill Count		x		x
Proper medication use	24-hour recall		x	x	x
Medication consolidation	24-hour recall		x	x	x
Treatment knowledge	Identification of drug purpose		x	x	
Clinical outcomes	HbA1c	chart	x		x
	systolic/diastolic blood pressure	in-person	x		x
Patient Covariates					
Medication Regimen Characteristics	Prescription medication, complexity (MRCI)	George, 2004	x		x
	drug class	George, 2004	x		x
Health status	Overall Health (Global)	PROMIS	x		x
	Comorbidities	Goodman, 2013	x		x
	Depression - SF (4 item)	PROMIS	x		

Regimen Education and Messaging in Diabetes (REMinD)

Health Literacy	NVS, Brief health literacy screener	Weiss, 2005; Chew, 2008	x		
Cognitive Status	MMSE	Folstein, 1975	x		
Patient Activation	CHAI	[name], 2017	x		x
Social Support	Tangible Support	Wolshin, 1997	x		
Sociodemographics	Age, sex, race/ethnicity, education, income, language, English proficiency, country of origin, time in US	self-report	x		
Patient Process Outcomes					
Patient/Provider Communication	CAHPS - Providers discuss medication decisions		x	x	x
Perceived Values of EHR and SMS Tools	Open-ended questions				x
Unmet needs and acceptability of tools	Open-ended questions				x
Personal challenges with medication regimen	Open-ended questions				x
System Process Outcomes					
Receipt of UMS Materials	Receipt of MedSheet (yes/no), UMS Sigs (yes/no), MedList (yes/no)	self-report, chart	x	x	x
Receipt of SMS text reminders	Receipt of SMS (yes/no)	self-report		x	x
Intervention impact on clinic practice	Provider Survey				x
Changes throughout intervention within clinic practice	Field notes with administrative staff				
Cost Outcomes					
Initial programming cost of EHR tools			x		
Programming maintenance costs for EHR					x
Running UMS technologies	Printer ink, paper, staff time		x		
SMS monthly costs			x		

9.10 COVID-19 Survey. We are proposing an optional sub-study to be conducted from a pool of existing studies conducted by [name] (LitCog (STU00026255), REMinD (STU00203777), COPD Multimorbidity (STU00201640), UMS Portal (STU00201639), and TAKE IT (STU00204465). Participants will be invited to participate

Regimen Education and Messaging in Diabetes (REMinD)

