based on the distribution of the outcome variable. The GLMMs will include random provider effects and fixed binary variables for SMS text reminder and EHR to denote the intervention groups and the usual care group (H1-4). We will include a fixed indicator variable for clinic in the GLMMs and any potential confounding covariates as noted above. Analyses will be performed using PROC GLMMIX in SAS (v.9.3) and lme4 package in R. Since understanding and adherence will be assessed for each medication, 2-level GLMM will be used with medications nested in participants. We will first test for differences in the outcomes between the EHR group and usual care (H1-3), followed by comparisons between EHR+SMS vs. usual care, and EHR vs. EHR+SMS to determine additional benefits of SMS texting (H4) by constructing contrasts.

Aim 2

We will include both literacy-by-arm and language-by-arm fixed interaction terms in the above GLMMs for all outcomes. We will use the corresponding model type III tests for fixed effects to determine significance of terms, and construct appropriate contrasts for pairwise comparisons for each literacy level and each language.

Aim 3

We will determine the extent to which the interventions were implemented as planned (a process evaluation) across each site and for all three study arms, in order to optimize the intervention for future dissemination opportunities.

Mixed methods will be employed using a convergent parallel design to obtain data on intervention implementation.

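### Hypothesis 5 concerns limited English proficiency, but the Aim 2 model tests language, so the hypothesised moderator has no specified test although it is collected at baseline

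*Combined protocol and SAP*

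**What the plan says.** Hypothesis 5 in Section 1.2 reads: "The intervention effects will be greater among those with limited literacy and English proficiency". Specific Aim 2 in Section 1.1 has no direction and names a different second moderator: "Determine if the effects of these UMS strategies vary by patients' literacy skills and language".

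The Aim 2 analysis in Section 11.1 follows the aim: "We will include both literacy-by-arm and language-by-arm fixed interaction terms in the above GLMMs for all outcomes". Significance is judged thus: "We will use the corresponding model type III tests for fixed effects to determine significance of terms". The plan will then "construct appropriate contrasts for pairwise comparisons for each literacy level and each language".

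The data collection table in Section 9.9 lists these self-reported baseline items: "Age, sex, race/ethnicity, education, income, language, English proficiency, country of origin, time in US". Language and English proficiency are therefore two variables, both collected once at baseline. Section 3.1 admits English or Spanish speakers, so language has two levels. The readable text gives no definition or cut-off for limited proficiency, and no alpha or power for Aim 2.

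**The concern.** Someone who speaks Spanish may or may not have limited English. Hypothesis 5 and the background in Section 2.1, which describes limited English proficiency as a barrier to safe medicine use, concern the second property. The model uses the first. If the benefit is larger in patients with limited proficiency, sorting by language puts proficient Spanish speakers in with the patients expected to gain most. This pulls the estimated interaction towards zero. A null language-by-arm result could then be read as evidence against Hypothesis 5, which the model did not test.

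The follow-up contrasts do not fill the gap. They compare arms within one literacy level or one language. Hypothesis 5 asks whether the effect in the limited group exceeds the effect in the adequate group. A significant contrast in one level beside a non-significant one in another does not answer that.

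**Working it through.** **Wording side by side**

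| Place | First moderator | Second moderator | Direction |
|---|---|---|---|
| Section 1.1, Specific Aim 2 | literacy | language | none |
| Section 1.2, Hypothesis 5 | limited literacy | limited English proficiency | larger in the limited group |
| Section 11.1, Aim 2 model | literacy-by-arm | language-by-arm | none |
| Section 9.9, baseline items | two literacy instruments | language and English proficiency, listed separately | not applicable |

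The literacy column agrees throughout; the second moderator does not.

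**Size of the dilution.** The plan has no power figure for Aim 2 to reproduce, so this is an illustration.

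*From the documents:* 240 analysed patients per arm and about 3 per physician (Section 11.1); 45% adherence in usual care and the upper ICC of 0.01 (Section 11.2). These give a variance of 0.45 × 0.55 = 0.2475 and a design effect of 1 + (3 − 1) × 0.01 = 1.02.

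*Assumed:* 30% of patients are Spanish-speaking; a fraction r of them has limited proficiency; no English speaker does. The true extra effect in the limited-proficiency group is 20 percentage points, equal in both UMS arms. The test is a 2-df Wald test at 5% on the risk-difference scale.

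*Step 1, interaction seen by language.* The extra effect is 20r points among Spanish speakers and 0 among English speakers. With r = 0.7 it is 20 × 0.7 = 14 points. This shrinkage does not depend on the 30%.

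*Step 2, variance.* With a share q in the limited (or Spanish-speaking) group, the within-arm difference between groups has variance V = (0.2475 × 1.02 / 240) × [1/q + 1/(1 − q)] = 0.001052 × [1/q + 1/(1 − q)].
- Language, q = 0.30: V = 0.001052 × 4.762 = 0.00501.
- Proficiency, q = 0.30 × 0.7 = 0.21: V = 0.001052 × 6.028 = 0.00634.

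*Step 3, noncentrality.* With an equal extra effect d in both UMS arms, λ = d² / (1.5V).
- Language: 0.14² / (1.5 × 0.00501) = 2.61, power 28%.
- Proficiency: 0.20² / (1.5 × 0.00634) = 4.21, power 43%.

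*Step 4, range over r.*

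| r | Interaction seen by language (points) | 2-df power, language | 2-df power, proficiency |
|---|---|---|---|
| 0.5 | 10 | 16% | 34% |
| 0.6 | 12 | 22% | 39% |
| 0.7 | 14 | 28% | 43% |
| 0.8 | 16 | 36% | 47% |
| 0.9 | 18 | 44% | 50% |
| 1.0 | 20 | 53% | 53% |

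The loss disappears only if every Spanish speaker has limited proficiency.

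*Step 5, precision of the repaired estimate.* For one UMS arm against usual care, the difference in effect between proficiency groups has variance 2V. At r = 0.7 its standard error is √(2 × 0.00634) = 0.113, so a 95% interval is about ± 1.96 × 0.113 = 22 points. The right moderator removes the dilution but does not make the test well powered.

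**The case against.** **The analysis fits the aim.** Specific Aim 2 itself says language, and Section 2.1 treats limited proficiency under a heading about language, so language may be the chosen stand-in. This stands in part: the analysis departs from Hypothesis 5, not from the aim, and for literacy there is no mismatch. But the documents do not say that language stands in for proficiency, and they collect both.

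**Exploratory interactions could cover it.** The Exploratory Analyses in Section 11.1 allow arm interactions with patient characteristics. Proficiency could be among them, but it is not named, and an unspecified exploratory term is a weak basis for a listed hypothesis.

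**The overlap is unknown.** This stands. If nearly all Spanish speakers in the trial have limited proficiency, the choice hardly matters.

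**Stronger readings that a reader might infer.**

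- *That type III tests necessarily waste power on a directional hypothesis.* The degrees of freedom are not stated. The models that Aim 2 extends use "fixed binary variables for SMS text reminder and EHR to denote the intervention groups and the usual care group", so a two-level moderator could give two 1-df tests and not one 2-df test. If the test does have 2 df, its power relative to a single contrast pooling both UMS arms depends on the pattern. Take λ = 7.85, where the 2-df test has 71%. With extra effects a and b in the two UMS arms, the pooled contrast keeps a fraction (a + b)² / [4(a² − ab + b²)] of λ. That is 1 for equal effects (80% power), 9/12 = 0.75 for a 2:1 ratio (68%), and 1/4 if only the SMS arm is modified (29%). Hypothesis 4 expects the two arms to differ on adherence. A pooled contrast is thus a trade-off, not a required repair.
- *That a non-directional test is itself an error.* Testing a directional hypothesis two-sided is normal practice, and the sign of the estimate gives the direction.
- *That the within-level contrasts carry a calculable false-positive rate.* No alpha is given for Aim 2. The contrasts cannot be independent either: the third arm comparison is the difference of the other two, and the literacy and language groups contain the same patients.

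**Conclusion.** The mismatch is real and internal to the document: Specific Aim 2 and the model use language, Hypothesis 5 uses English proficiency, and proficiency is collected but has no specified test. The literacy half of Hypothesis 5 is unaffected.

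The dilution is proportional to the share of Spanish speakers whose English is adequate. In the central illustration it costs 6 of 20 points of interaction and about 15 points of power (43% − 28%). Over r from 0.5 to 1.0 the power cost runs from about 18 points to nil. These figures rest on the assumed Spanish-speaking share, overlap, effect size, equal modification in both UMS arms and a 2-df test. The direction of the bias needs only that proficiency is the true moderator and that some Spanish speakers are proficient.

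The documents do not support a finding that the type III approach is wrong in itself. The defect is the unnamed moderator, together with the lack of a stated comparison of limited with adequate groups.

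**What to change.** In Section 11.1, Aim 2:

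1. Name the English-proficiency-by-arm interaction, limited against adequate, as the test of the second half of Hypothesis 5. State which baseline item defines it and the cut-off.
2. Keep language-by-arm as the analysis for Specific Aim 2, and say that the two answer different questions.
3. For literacy and for proficiency, judge Hypothesis 5 by the difference between limited and adequate groups in each UMS-versus-usual-care effect. Report its sign and confidence interval, and state the scale and the alpha. Do not base the conclusion on arm contrasts within levels.
4. State that precision will be limited.

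The cost is SAP wording and one more interaction term per outcome; no new data are needed. Proficiency and language overlap, so the proficiency interaction should be fitted in a separate model and not beside language-by-arm, where the two would compete for the same information. The type III tests can stay as planned.

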Based on our 2014 findings examining the UMS in pharmacy practice [R01HS017687; R01HS016435], We expect 45% of usual care patients to be adherent at 6 months (Table 5). With prior-specified assumptions, we will have 85%-88% power to detect a minimum absolute difference between study arms of 14%. With the sample size set by the primary outcome of adherence at 6 months, we also show overall estimated detectable pairwise differences for secondary outcomes of demonstrated proper use and consolidation at 80% power (Aim 1, H1-4) based on usual care estimates for proper use and regimen consolidation.

11.3 **Protocol to ensure confidentiality:**

Each subject will tracked using an Access database. Identifiers and other related information for coordinating research activities (recruitment outcome, research interview call log and interview visit schedule, etc.) will be password protected and kept on the secure Northwestern network drive. Only the PI, project manager, and RAs will have access this database.

Several methods will be employed to reduce the risk of breach of confidentiality. A study identification number will be assigned to each subject in the study. The research data collected and stored will have the study identification number and no other identifying information on it. The consent forms and the de-identified study data will be kept in a separate locked file cabinet at the same location. Using this method, if someone were to gain illegal access to the locked filing cabinet with study data, they would have no way to link this data to any identifying information. Mt. Sinai will do the same with their participants, under their own IRB.

11.4 **Quality Assurance:**

Training will begin after surveys and interview protocols have been refined and standardized. The project manager will lead sessions to orient the research staff to the surveys and study protocols (e.g., interview process, use of laptop PCs, data security). Training the entire research staff at once, via a web conference, to ensure uniform administration of the study protocols and interviews. Practice of the interviews will proceed independently at the participating institutions. All interviewers will be required to demonstrate competence in survey administration and to pass a certification test.

Regimen Education and Messaging in Diabetes (REMinD)

11.5 Study-wide data management:

Data Access: Only authorized personnel listed on each institution's IRB will have access to the data.

Data Storage: The research staff at NU and Mt. Sinai will collect data through the Northwestern RedCap survey platform. Data will be stored in REDCap, a secure, web-based application, and on the Northwestern secure servers for the length of the study. Data from Mt Sinai's EHR extractions will be uploaded to Northwestern's Sharepoint site specific to this study. The Project Manager or Data Analyst will download the data from REDCap monthly and save to the "Analytic" folder within the project folder on the FSM department servers which are located in a HIPAA compliant data center. These data files do not contain any identifiable information, and are identified by project staff by an assigned study ID. No identifiability information are entered into REDCap. Upon completion of all study activities, a final de-identified dataset will be created. This dataset will be stored indefinitely on the GIM server for secondary analyses. Only authorized personnel will have access to the dataset. All identifiable information will be deleted upon completion of the study

Data Coordination Center (Northwestern): The project manager and data analyst at NU will combine the data and maintain the master data file containing all data from each location, create a data dictionary, and be responsible for data cleaning and providing updated data to study investigators when requested.

COVID-19 Survey: By extending each of these studies (LitCog (STU00026255), REMinD (STU00203777), COPD Multimorbidity (STU00201640), UMS Portal (STU00201639), and TAKE IT (STU00204465)) to capture an additional patient-reported outcome related to one's knowledge, attitudes and behaviors related to COVID-19, we can link participants' responses to this longitudinal survey to a minimum data set of participant characteristics that include demographic, socioeconomic, cognitive (including health literacy) and health behavioral characteristics. We will then be able to investigate determinants of COVID-19 knowledge, attitudes and behaviors without duplicating data collection efforts for these variables.

[name] will be analyzing data from the Wave 1 health literacy items.

[name] will be analyzing data to better understand alcohol use in older adults during the COVID-19 pandemic. [name] is an assistant professor of neurology and will be analyzing the PROMIS Sleep items to better understand the relationship between COVID-19 and sleep disturbance.

RCs will conduct interviews by telephone using REDCap survey software. [name] (analyst) will oversee database structure & quality assurance. Participants will complete 5 phone interviews with RCs.

Regimen Education and Messaging in Diabetes (REMinD)

Statistical analyses will be led by [name], and all analyses will be conducted with SAS 9.4 (Cary, NC). Using data from the C3 cohort, participants' perceived levels of stress has been assessed from the initial onset of the outbreak (March 13-20; C3 W1), through its rapid acceleration (March 27-April 3; C3 W2) and apex phases (May 1-22; C3 W3), and the flattening phase (July 15- August 15; C3 W4) of the COVID-19 pandemic. The additional surveys provides the opportunity to continually assess persistent stress over a span of time that likely will include the pandemic's expected, slow recovery, an anticipated second wave in the fall/winter of 2020/2021, and its eventual recovery as well. Also during this time, there may be new treatments available, as well as a vaccine for COVID-19. Initial models will examine associations between perceived stress as a result of COVID-19 and health and healthcare outcomes over time among C3 participants. As perceived stress, health and lifestyle behaviors are expected to change over time, we will use GLMMs to examine the relationship between stress, and outcomes (diet, alcohol use, smoking, physical activity, diet, weight gain, sleep, social isolation, treatment adherence, self-reported health status) using stress as a time-varying covariate. For data from the EHR, we will assess routine health care use.

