in an optional one-time brief (5-10 minute) telephone survey to capture one additional outcome pertaining to their knowledge, attitudes, and beliefs about the COVID-19 outbreak in March 2020. They will also be asked a series of patient-reported health literacy items. This new data will be linked with participant characteristics from the parent study. Participants who complete the COVID-19 survey will receive a \$10 gift card in the mail.

Recruitment will be done by phone by trained Northwestern RAs. We will contact anyone who has indicated that they were willing to be contacted for future studies run by [name] on the consent form. Verbal consent will be obtained prior to completing the one time brief (5-10 minute) telephone survey.

Waves 2-4:

From the same pool of existing studies included in Wave 1, any participants who completed the Wave 1 COVID-19 survey will be contacted and invited to participate in up to 3 additional telephone surveys (10-30 minutes each) over the course of 4 months to continue to evaluate knowledge, attitudes, and beliefs over time about the ongoing COVID-19 pandemic. Participants who complete the follow-up interviews will receive a \$10 gift card in the mail for wave 2 and a \$15 gift card for waves 3 and 4 (per survey), for a total of up to \$40 for the follow-up activities. For wave 3 and 4, we increased the participant compensation from \$10 to \$15 due to the longer survey administered at this time point.

Recruitment will be done by phone by trained Northwestern RAs. We will invite anyone who has indicated that they were willing to be contacted for future studies run by [name] on the consent form and who completed the Wave 1 survey. Verbal consent for the follow up waves will be obtained prior to completing the Wave 2 telephone survey (initiated 2 weeks after Wave 1). Participants who consent to these follow-up activities will be re-contacted for completion of Waves 3 and 4 at 1 month and 3 months post-wave 2.

Waves 5-9:

In March 2020, we recruited a subset of the REMinD cohort (n=136), and patients enrolled in four other studies (n=537; Total N=673) to form the Chicago COVID-19 Comorbidities (C3) cohort study. We initially completed four phone interviews (described above) with them to better understand how older adults with underlying health conditions, at greater risk for COVID-19 complications, were responding and taking action (or not) to prevent infection and disease spread.

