We will now continue our investigation to better understand the longer-term impact of COVID-19. From the same pool of existing studies, any participants who completed the Wave 1 COVID-19 survey will be contacted and invited to participate in up to 5 additional telephone surveys occurring every 4 months. Interviews will collect information on participants' responses to COVID-19 and changes in lifestyle behaviors, healthcare utilization, physical and mental health, access and adherence to treatment, socioeconomic circumstances and clinical outcomes. We will also collect data from the medical record and pharmacy record abstractions.

Regimen Education and Messaging in Diabetes (REMinD)

Participants who complete additional telephone surveys will receive compensation in the mail. See section 22.2 for further details.

Data from all waves of the COVID-19 telephone surveys will be captured in REDCap.

this study (STU00208130) in order to create a final and complete dataset..

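### The COVID-19 cohort models do not separate between-person from within-person association with stress; a single stress term would mix the two

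*Combined protocol and SAP*

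**What the plan says.** The statistical plan for the pooled COVID-19 (C3) cohort is a short paragraph at the end of section 11.5 (Study-wide data management, COVID-19 Survey).

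- Its aim is modest: "Initial models will examine associations between perceived stress as a result of COVID-19 and health and healthcare outcomes over time among C3 participants".
- Its reason for a longitudinal model is that both sides move: "As perceived stress, health and lifestyle behaviors are expected to change over time".
- Its method is: "we will use GLMMs to examine the relationship between stress, and outcomes", "using stress as a time-varying covariate". The listed outcomes include diet, alcohol, smoking, activity, sleep, isolation, treatment adherence and self-rated health.
- The paragraph gives no random-effects structure, link functions, adjustment covariates, wave term or parent-study term, and does not say how stress is coded beyond varying with time.

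On the data, section 9.10 says that "we recruited a subset of the REMinD cohort (n=136), and patients enrolled in four other studies (n=537; Total N=673" in all. Section 11.5 reports that "participants' perceived levels of stress has been assessed from the initial onset of the outbreak (March 13-20; C3 W1" and then through three further waves. Section 9.10 adds "up to 5 additional telephone surveys occurring every 4 months". Stress may therefore be available at up to 4 + 5 = 9 waves.

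**The concern.** A covariate that changes from wave to wave carries two kinds of information. One is whether people with higher average stress differ in outcome from people with lower average stress. The other is whether the same person does differently in waves when their own stress is above its usual level. The first is open to every stable difference between people, such as income, literacy or prior illness. The second is not, although it remains open to things that change over time.

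A random-intercept model with one undivided stress term assumes that the two slopes are equal and returns a weighted average of them. If they differ, the coefficient describes neither. Because the plan justifies the model by change over time, readers are likely to take the coefficient as longitudinal when part of it is cross-sectional.

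Pooling adds a smaller point. The cohort draws on five parent studies. One of them, REMinD, randomises providers to arms intended to raise adherence, and treatment adherence is one of the cohort's outcomes. The paragraph does not say whether parent study or arm enters the models.

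**Working it through.** **No plan figure to reproduce.** The documents give no sample size, power or error rate for these models. The one checkable sum is the cohort size: 136 + 537 = 673, which is correct.

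**Inputs.** From the documents: 673 people and T between 5 (Waves 5-9) and 9 (all waves, if the outcomes were measured in each). Assumed, because the documents are silent: intraclass correlation of stress ρx = 0.4-0.6; residual intraclass correlation of the outcome ρy = 0.3-0.5; a linear outcome; every person seen at every wave; a random intercept; one stress term.

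**Formula.** Under generalized least squares,

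single coefficient = (1 − w) × within slope + w × between slope,

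with w = λB / (W + λB), where λ = (1 − ρy) / [(1 − ρy) + Tρy], W = (T − 1)(1 − ρx) and B = Tρx + (1 − ρx).

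**Between-person weight at the ends of the assumed range.**

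- T = 5, ρx = 0.4, ρy = 0.5: λ = 0.5/3.0 = 0.167, W = 2.4, B = 2.6, so w = 0.433/2.833 = 0.153.
- T = 5, ρx = 0.6, ρy = 0.3: λ = 0.7/2.2 = 0.318, W = 1.6, B = 3.4, so w = 1.082/2.682 = 0.403.
- T = 9, ρx = 0.4, ρy = 0.5: λ = 0.5/5.0 = 0.100, W = 4.8, B = 4.2, so w = 0.420/5.220 = 0.080.
- T = 9, ρx = 0.6, ρy = 0.3: λ = 0.7/3.4 = 0.206, W = 3.2, B = 5.8, so w = 1.194/4.394 = 0.272.

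**Wider assumptions.** With ρx from 0.3 to 0.8 and ρy from 0.2 to 0.8, w runs from 0.036 to 0.700 for T = 5 and from 0.016 to 0.587 for T = 9. The mix is large when stress is stable within people and the outcome is labile. It is close to nil in the opposite case with nine waves.

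**Simulation check.** 500 runs per setting, 673 people, known variance components, two-sided 5% tests, between slope 0.3:

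- Within slope 0, ρx = 0.6, ρy = 0.4, T = 5: the single term averages 0.099 (formula: 0.329 × 0.3 = 0.099) and is significant in 100% of runs. With two terms, the within coefficient averages 0.00 and is significant in 5.4%; the between coefficient averages 0.30.
- The same with T = 9: the single term averages 0.062 and is significant in 98%.
- Within slope 0, ρx = 0.3, ρy = 0.8, T = 9: the single term averages 0.005.
- Within slope also 0.3, ρx = 0.6, ρy = 0.4, T = 5: the single term averages 0.30, so there is no distortion.

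**Cost of splitting.** The information on the within slope falls from W + λB to W, so its standard error grows by 1/√(1 − w). At T = 5 this is 1/√0.847 = 1.09 to 1/√0.597 = 1.29. At T = 9 it is 1/√0.920 = 1.04 to 1/√0.728 = 1.17.

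**The case against.** The strongest reply is that the plan promises only associations, in models it calls initial, and that a blended coefficient is still an association. That stands. A reader might infer that the analysis fails to answer what a rise in stress does to a person. The documents do not support that charge, because they never pose the question. Section 9.10 gives the aim of the later waves as the longer-term impact of COVID-19 and does not name stress as the cause under study.

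A reader might also infer that the plan has chosen a single undivided term with a random intercept. It has not said so. A time-varying covariate is one that is updated at each wave, and the paragraph is silent on centring and on random effects. Likewise, since it lists no covariates at all, the lack of a parent-study term cannot be read as a decision. Section 11.5 says that demographic, socioeconomic, cognitive and health-behaviour characteristics will be linked, so adjustment for stable confounders is possible, though not promised.

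Three limits on size also stand. The intraclass correlations are assumed. On the narrower assumptions most of the weight is within-person (0.60-0.85 with 5 waves, 0.73-0.92 with 9). Several outcomes, such as smoking, are unlikely to be linear, and waves will be missed; both change the weights but not the principle. On pooling, the documents show randomised arms aimed at adherence only for REMinD, 136 of 673 people (about 20%); the designs of the other four studies are not described.

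What the reply does not remove is that a model motivated by change over time needs to say which association its coefficient measures, and that the repeated stress measurements allow the two to be separated.

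**Conclusion.** The point holds as a low-cost improvement. As described, the method does not separate between-person from within-person association. If carried out with one stress term and a random intercept, it would give the between-person slope a weight of about 0.15-0.40 with 5 waves or 0.08-0.27 with 9, under the stated assumptions; wider assumptions span about 0.02-0.70. The resulting bias is that weight times the difference between the two slopes, so it is zero when they agree.

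Two stronger conclusions do not follow. The single coefficient is not useless: it is a valid but mixed association. Nor would splitting it reveal the causal effect of stress, since time-varying confounding and reverse direction within a wave would remain. The issue is confined to an optional observational sub-study and has no bearing on the trial's primary analysis of adherence at six months by arm (section 11.1).

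**What to change.** Keep the planned mixed models and amend the paragraph in section 11.5 as follows.

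1. Replace stress by two terms: the person's mean stress over the waves attended, and each wave's deviation from that mean.
2. Report both coefficients, labelled as between-person and within-person associations. Do not call the deviation term a causal effect.
3. Add fixed effects for wave, so that shifts shared by the whole cohort across pandemic phases are not credited to individual stress. Add fixed effects for parent study and, for REMinD patients, study arm.
4. State the random effects and the link function for each outcome.
5. Optionally, repeat the models with stress from the previous wave as a sensitivity check on direction.

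The cost is one derived variable and a few lines of SAS, with no new data. The within-person interval becomes wider than that of the single term, by about 9-29% with 5 waves or 4-17% with 9 under the narrower assumptions. The optional lagged model also loses each person's first wave.
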